#### **INTERVENTIONS**

**Presentation:** The outreach presentation will last 75 minutes with an additional 15 minutes for caregiver questions. The presentations will occur in the evening via Zoom. The presentation will include information about identifying anxiety disorders, strategies for caregivers to help their youth with anxiety, evidence-based practices to treat youth anxiety, and strategies for finding a therapist who uses cognitive behavior therapy with exposures. The text on the presentations is written at a 5.3 grade reading level. Presentations will incorporate stigma reduction strategies, such as education to dispel myths, and behavioral decision-making tools to elicit hope, empowerment, and motivation.

**Researcher-Only condition:** The researcher-facilitated presentation, led by two clinical psychology graduate students, will be the same for all schools.

**Key opinion leader:** The key opinion leader (KOL) co-facilitated presentations will include the same core principles as the researcher-facilitated presentation but may vary by school in terms of specific examples and content emphasized based on KOL feedback. A caregiver KOL from the local community will co-facilitate the presentation with a clinical psychology graduate researcher. To select the KOLs, the principal investigator will contact the school PTA (or a similar parent group), and PTAs will be asked, "please nominate a caregiver who is well-known and respected within your community, and who reflects the diversity of the school as a whole." The PI will meet with the KOLs to review the presentation and to engage them in championing cognitive behavior therapy for youth anxiety.

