### **Exploratory outcome measures:**

- 7. Change From Pre-Presentation to Post-Presentation in Barriers to Seeking Treatment [Time Frame: pre-presentation; post-presentation (within 1 week after the presentation)]

  The Barriers to Seeking Treatment questionnaire asks participants to indicate whether they agree with 21 potential barriers to treatment (Heeringa et al., 2004). A count of the total number of barriers will be used in analyses.
- 8. Change From Pre-Presentation to 3-Month Follow-Up in Barriers to Seeking Treatment [Time Frame: pre-presentation; 3-month follow-up]

The Barriers to Seeking Treatment questionnaire asks participants to indicate whether they agree with 21 potential barriers to treatment (yes/no; Heeringa et al., 2004). A count of the total number of barriers will be used in analyses.

9. Client Satisfaction Questionnaire [Time Frame: post-presentation (within 1 week after the presentation)]

The Client Satisfaction Questionnaire assesses participants' satisfaction with the presentation. Items are rated on scale ranging from 1 to 4. Items are summed; higher composite scores indicate greater program satisfaction.

10. Relatability Evaluation [Time Frame: post-presentation (within 1 week after the presentation)]

The Relatability Evaluation will be used to evaluate participants' impression of the presenter. Participants will rate each presenter (scale ranging from 1 to 5) on 10 items associated with aspects of key opinion leaders: relatable, likeable, similar, think similarly, similar beliefs, credible, trustworthy, understanding of the local community, familiar, and friendship. Items are summed; higher composite scores indicate that the presenter is more relatable.

11. Brief Revised Child Anxiety and Depression Scale-Parent Version [Time Frame: prepresentation]

The total anxiety scale (15 items) from the Brief Revised Child Anxiety and Depression Scale-Parent Version will be used to assess youth anxiety (Ebesutani et al., 2017). Participants rate items on a scale from 0 (*never*) to 3 (*always*). Items are summed; higher scores indicate higher levels of anxiety.

12. Demographics [Time Frame: pre-presentation]

A demographics questionnaire will assess caregiver and youth age, gender, race, ethnicity, and nativity; caregiver level of education, income, and religion; and youth health insurance status.

13. Content Checklist [Time Frame: during the 1.5 hour presentation]

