A content checklist will assess the core components of the presentation, as well as presenter and audience member self-disclosure about experiencing receiving therapy for themselves or their child (yes/no). Self-disclosure will be considered to have been made if either the presenter or an audience member self-discloses about their experiences.

14. Qualitative Interview [Time Frame: 3-month follow-up]

A qualitative interview will ask participants about the following topics: (1) their perception of presenters; (2) ways in which the presenters affected their decision to seek treatment; (3) factors they considered when seeking treatment; (4) strategies they have used from the presentation; (5) their perception of exposure therapy; and (6) general ways that the mental health system could be improved to improve access to therapy.

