researcher co-facilitator) as a person-level predictor; and time (pre- and post-presentation) as an observation-level predictor. In separate multilevel models, (a) intention to seek CBT, (b) Therapy Subjective Norms Questionnaire—CBT, (c) Caregiver Attitudes about CBT, (d) Parents' Internalized Stigma of Mental Illness Scale, and (e) Parent Engagement in Evidence-Based Services Questionnaire-Knowledge subscale will be regressed on time, condition, and the interaction between time and condition; a random intercept will be included in all five multilevel models. A binary logistic regression will be conducted with CBT service seeking at the threemonth follow-up (Treatment Seeking Evaluation - Actual CBT seeking) entered as the dependent variable, condition entered as the independent variable, and youth anxiety (Brief Revised Child Anxiety and Depression Scale-Total Anxiety) entered as a control variable. Ttests will be used to compare difference between conditions for each item on the Relatability Evaluation of the principal investigator. This study will examine caregiver demographic factors, youth anxiety (Brief Revised Child Anxiety and Depression Scale-Total Anxiety), racial similarity to the presenter (Demographics, same race), and self-disclosure (Content Checklist, selfdisclosure), as potential moderators of the effect of presentation condition on intention to seek CBT. In separate multilevel models, intention to seek CBT will be regressed on time, condition, each potential moderators, and their three-way interaction.

**Qualitative Analyses:** The transcribed qualitative interviews will be entered into NVivo software for analysis. Qualitative analyses will use a direct content analysis approach (Hsieh & Shannon, 2016). The coding team will create an initial codebook using the primary topics asked in the qualitative interviews. Additional codes will be added to code text that does not fit into the initial categories, either to split the initial codes into two, or to create new codes. Coding will occur through a consensus process in which each transcript will be coded independently by two raters, who will arrive at consensus through discussion (Hill et al., 2005). Thematic responses will be examined by both condition and by whether the caregiver has sought treatment for their youth (4 groups total).

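### Self-disclosure is recorded during the session and can be affected by condition, so its interaction with condition cannot be read as moderation; racial similarity needs a named presenter

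*Combined protocol and SAP*

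**What the plan says.** The quantitative part of Planned Analyses names "self-disclosure (Content Checklist, selfdisclosure), as potential moderators" of the condition effect on intention, alongside caregiver demographics, youth anxiety and "racial similarity to the presenter (Demographics, same race". There is one model per moderator: "intention to seek CBT will be regressed on time, condition, each potential moderators, and their three-way interaction".

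The disclosure variable is item 13 of the exploratory measures: "Content Checklist [Time Frame: during the 1.5 hour presentation". Its coding rule is: "Self-disclosure will be considered to have been made if either the presenter or an audience member self-discloses about their experiences".

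Under Interventions, the KOL arm is described thus: "A caregiver KOL from the local community will co-facilitate the presentation with a clinical psychology graduate researcher". The researcher-only presentation is "led by two clinical psychology graduate students, will be the same for all schools". Hypothesis 3 shows the principal investigator presenting in both conditions.

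The document does not say that disclosure may depend on condition, has no rule for empty cells, does not give the number of schools, and does not say which of the two presenters defines racial similarity.

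**The concern.** A moderator analysis asks whether the effect of assignment differs between groups that exist independently of assignment. Self-disclosure does not define such groups. It happens inside the intervention, after randomization, and one of its two sources is the presenters, whom the condition determines. KOL sessions that contain disclosure and researcher-only sessions that contain it may have come to do so by different routes. Comparing them is no longer a randomized comparison.

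The variable also belongs to the session. Information about it grows with the number of sessions, not with the 180 caregivers, and a small trial may have no session at all in one of the four condition-by-disclosure cells.

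At stake is interpretation. A non-zero three-way term could be reported as showing where a KOL works better or worse, when it reflects only how disclosure arose in each arm.

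**Working it through.** **Plan's own figure.** None exists for the moderator analyses. The Sample size section covers other tests, so there is nothing to reproduce.

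**Form of the test.** With two time points, and taking lower-order terms as included, the time-by-condition-by-moderator term equals the condition-by-moderator term on the pre-post change.

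**1. Empty cells (self-disclosure).** Assumptions: one session per school, K sessions per arm, independent disclosure with probability p in the KOL arm and q in the researcher-only arm. All four cells are occupied only if each arm has at least one session of each kind:

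P(empty cell) = 1 - [1 - p^K - (1-p)^K] × [1 - q^K - (1-q)^K]

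- K = 6, p = 0.9, q = 0.3: 1 - (1 - 0.5314 - 0.0000)(1 - 0.1176 - 0.0007) = 1 - 0.4686 × 0.8816 = **0.59**.
- K = 6, p = 0.7, q = 0.4: 1 - (1 - 0.1176 - 0.0007)(1 - 0.0467 - 0.0041) = 1 - 0.8816 × 0.9492 = **0.16**.

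Other assumed inputs:

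| p / q | 5 per arm | 10 per arm |
|---|---|---|
| 0.9 / 0.1 | 0.83 | 0.58 |
| 0.8 / 0.2 | 0.55 | 0.20 |
| 0.7 / 0.3 | 0.31 | 0.06 |
| 0.5 / 0.5 | 0.12 | about 0 |

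**2. Bias when the term can be estimated (self-disclosure).** Simulation with a true condition effect of 0.30 SD in every session, so the true interaction is 0.

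- *Presenter disclosure differs by arm; audience disclosure depends on a session trait that also shifts change.* With presenter disclosure at 80% versus 10%, the estimated interaction is -0.047, -0.095 and -0.147 when one SD of the trait shifts change by 0.1, 0.2 and 0.3 SD. At 90% versus 0% and a shift of 0.3 it is -0.194. In the -0.147 case the apparent condition effect is 0.300 in non-disclosing sessions and 0.300 - 0.147 = 0.153 in disclosing ones, although it is the same in both.
- *Presenter disclosure equal in both arms.* With 0% or 30% in both, the interaction is 0.003 or -0.001.
- *One trait drives all disclosure in both arms and only its overall level differs by arm.* The interaction stays small (0.00 to 0.06), but the condition effect in non-disclosing sessions falls from 0.30 to about 0.06 to 0.19.

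**3. Racial similarity.** Assumed scenario: two groups; half the schools have 20% and half 80% of caregivers in group 1; the KOL belongs to the school's majority; the researcher is in group 1; being in group 1 adds 0.3 SD to change; the condition effect is 0.30 with no moderation.

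- *Match to the arm-specific co-presenter.* In the researcher-only arm, match is the same as being in group 1, so mean change is 0.30 if matched and 0 if not. In the KOL arm, matched and unmatched caregivers are each half group 1, so mean change is 0.30 + 0.3 × 0.5 = 0.45 in both. The apparent condition effect is 0.45 - 0.30 = 0.15 if matched and 0.45 - 0 = 0.45 if not. The interaction is 0.15 - 0.45 = **-0.30**, and simulation gives -0.304.
- *Match to a researcher common to both arms.* Match is fixed at baseline and simulation gives -0.001.

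Match varies between caregivers within a session, so the empty-cell calculation in step 1 does not carry over to it.

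**The case against.** The strongest reply has four parts.

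*Disclosure is not shown to follow from condition.* A reader might infer that assignment produces disclosure because a KOL is a local parent. The text does not support this. Audience disclosure counts in both arms, every attendee is a caregiver, graduate students may speak of their own therapy, and KOLs are nominated for standing in the community and for reflecting its diversity, not for experience of therapy. This stands: the documents support only that disclosure can be affected by condition. That is enough, because a variable measured after randomization and open to influence by assignment does not define a baseline subgroup.

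*Racial match may be sound.* A reader might infer that it shares the same defect. The plan says only the presenter. If the principal investigator is meant, match is a baseline variable and the objection fails. If the co-presenter or either presenter is meant, match depends on condition. The wording does not settle this: the same section names the principal investigator when it means her, for the relatability comparisons. What stands against the plan is the ambiguity.

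*The numbers are assumed.* This also stands. Across plausible inputs the empty-cell probability runs from negligible to high, and the bias in the interaction can be close to zero.

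*No aim or hypothesis concerns moderation.* Correct, and it limits how much weight the point can carry. False-positive inflation from unmodelled clustering by school is a separate matter and is not counted here.

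**Conclusion.** The concern holds for self-disclosure as a point of interpretation and, with few schools, of estimability. The variable is post-randomization, session-level and open to influence by condition, so its interaction with condition cannot be interpreted as moderation. Under the scenarios above, a spurious interaction of about -0.05 to -0.19 SD is possible against a true condition effect of 0.30 SD, and the chance of an empty cell runs from about 0 to 0.83 for 5 to 10 sessions per arm. These figures rest on assumed school numbers, disclosure rates and trait effects, none of which the document gives.

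For racial similarity the finding is conditional. Under one reading it is a valid baseline moderator, and under the other it depends on condition. It would be wrong to conclude that it cannot be estimated.

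A reader might extend the point to the main results. The documents give no ground for that: neither the time-by-condition models nor the three-month logistic regression contains disclosure or racial match. Only the moderator analyses are affected.

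**What to change.** - Remove self-disclosure from the moderator list. Report its frequency by condition, with counts by condition and school, and examine it only as an exploratory process variable, either descriptively or in a school-level mediation analysis.
- State which presenter defines racial similarity. If it is a researcher who presents in both arms, it may stay as a moderator, with two notes: it then amounts to an indicator of caregiver race, which overlaps with the demographic moderators, and Hypothesis 3 shows the principal investigator in both conditions but not necessarily in every session. If it is the co-presenter or either presenter, report match descriptively within arm.

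The cost is a few lines of wording. No data collection changes. At the date given in the plan, 17 participants had pre/post data and nothing had been analysed, so the change could be made without knowledge of results.

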## **Primary Aims**

**Aim 1:** Test the relative effects of researcher-only and KOL conditions on changing caregivers' intention to seek CBT for their youth, and actual CBT seeking at three-month follow up.

*Hypothesis 1a:* Relative to the researcher-only condition, the KOL condition will result in a greater increase in intention to seek CBT with exposures.

*Hypothesis 1b:* Relative to the researcher-only condition, the KOL condition will result in a greater seeking of CBT with exposures for their youth at the three-month follow-up.

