#### Criteria for exclusion:

None

**Sample size:** For aim 1 and 3, a Monte Carlo-based power estimate was derived using Mplus with 10,000 replications. For the sample size of 180, assuming a Type I error rate of 5%, a two-tailed test, statistical power was .83 to detect a medium-sized effect (r = .30) of randomization group on longitudinal changes, given an expectation of a small (r = .15) effect for the control group. For aim 2, power was calculated using G\*Power. Given the brevity of the three-month follow-up questionnaire, a 10% attrition rate was assumed. Assuming a Type I error rate of 5%,

a two-tailed test, and a 25% rate of seeking EBPs in the researcher-only condition, statistical power was .82 to detect a medium effect (odd ratio = 1.72).

**Randomization:** Participants will be cluster randomized by school using restricted randomization with Excel's random number generator.

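### The moderator models list no two-way interactions; fitted as written, an effect on change can show up as moderation

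*Combined protocol and SAP*

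**What the plan says.** Two model statements stand close together in Planned Analyses (Quantitative Analyses).

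- **Five outcome models.** Each outcome "will be regressed on time, condition, and the interaction between time and condition", and "a random intercept will be included in all five multilevel models".
- **Moderator models.** Caregiver demographics, youth anxiety, racial similarity to the presenter and self-disclosure are examined "as potential moderators of the effect of presentation condition on intention to seek CBT". There, "intention to seek CBT will be regressed on time, condition, each potential moderators, and their three-way interaction".

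The moderator sentence names three main effects and one three-way term. It does not name time × condition, time × moderator or condition × moderator. The document gives no numeric coding for time, condition or any categorical moderator, and no centring rule for the anxiety sum (15 items scored 0–3, described under Exploratory outcome measures).

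Hypothesis 1a, under Primary Aims, expects a non-zero time × condition effect: "Relative to the researcher-only condition, the KOL condition will result in a greater increase in intention to seek CBT with exposures".

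**The concern.** A three-way interaction measures moderation of the condition effect on change only when the lower-order interactions are also in the model. If time × condition is left out, the three-way column is the only one that can carry a difference in change between arms, so it takes up part of that difference. Hypothesis 1a predicts exactly such a difference. Leaving out time × moderator opens a second route: if, say, caregivers of more anxious youth change more in both arms, this too loads on the three-way term.

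At stake are statements about which caregivers benefit more from a key opinion leader. They concern intention to seek CBT, which is a primary outcome, and they could be produced by the model specification rather than by the data.

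**Working it through.** **The plan's own figure.** None is given for the moderator models. The nearest is in the Sample size paragraph, which for N = 180 and a 5% two-sided test reports: "statistical power was .83 to detect a medium-sized effect (r = .30) of randomization group on longitudinal changes". The control arm is assigned r = .15. With d = 2r/√(1−r²), r = .30 gives 0.629 and r = .15 gives 0.303, a difference of 0.326 SD. On change scores (SD = √(2(1−ρ)), 90 per arm) this difference has power .59, .68, .80 and .93 for pre-post correlation ρ = .5, .6, .7 and .8. So .83 needs an unstated ρ a little above .7. The Mplus run itself cannot be rebuilt from what is given. On this reading, a condition effect on change of δ = 0.3 SD is close to the planned one.

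**Inputs.** From the documents: N = 180, 5% two-sided, two time points, random intercept (stated for the five outcome models and taken to apply here). Assumed: 90 per arm, unit SD, ρ = .5–.7, moderator m independent of condition c, anxiety mean 12 and SD 7, no school clustering. The true three-way effect is zero throughout.

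**Leak from the condition effect (time and condition 0/1, m uncentred).** With two time points, the random-intercept fit splits into a regression on within-person differences (variance 1−ρ) and one on sums (variance 1+ρ).

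- In the difference part, the three-way column is c·m, and a true effect δ·c gives it slope δ·cov(cm, c)/var(cm).
- In the sum part, the condition main effect absorbs δ·c, so the slope is 0.
- The two parts combine with weights a = var(cm)/[2(1−ρ)] and b = 0.25·var(m)/[2(1+ρ)].
- Expected three-way estimate = δ × cov(cm, c)/var(cm) × a/(a+b), and SE = 1/√(180(a+b)).
- With z = estimate/SE, false-positive rate = Φ(z−1.96) + Φ(−z−1.96).

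For a binary moderator with proportion p coded 1, var(cm) = 0.5p − 0.25p² and cov(cm, c)/var(cm) = 1/(2−p).

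Worked case, p = .5, ρ = .6, δ = 0.3:

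- var(cm) = 0.1875, so a = 0.1875/0.8 = 0.234.
- b = 0.0625/3.2 = 0.0195, so a/(a+b) = 0.923.
- Leak = 0.667 × 0.923 = 0.615 of the condition effect. The estimate is 0.185.
- SE = 1/√(180 × 0.254) = 0.148 and z = 1.25. The rate is 24%.

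Simulation gives 22–23% for this case. It also gives an estimate of 0.25 for a true δ of 0.4 (a leak of about 0.6), unchanged at N = 20,000, so this is bias and not small-sample noise.

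| Moderator, δ = 0.3 SD | Formula, ρ = .5 / .6 / .7 | Simulated, ρ = .5–.7 |
|---|---|---|
| Binary, 30% coded 1 | 12 / 15 / 18% | 12–18% |
| Binary, 50% coded 1 | 20 / 24 / 31% | 20–31% |
| Binary, 70% coded 1 | 30 / 36 / 46% | 29–46% |
| Anxiety sum, uncentred | 32 / 39 / 50% | 34–53% |
| All two-way terms included | – | about 4–6% |

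The 30% and 70% rows can be the same moderator with the reference category switched. At ρ = .6, as δ goes through 0, 0.2, 0.3, 0.4 and 0.6 SD, simulated rates are 5, 14, 22, 38 and 66% for the 50% binary moderator and 4, 20, 41, 61 and 91% for uncentred anxiety.

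**Moderator mean-centred.** Then cov(cm, c) = 0 and the condition effect no longer leaks. Simulated rates are 4–6% at every δ.

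**Leak from a time × moderator effect (δ = 0, m centred, time and condition 0/1).** Now cov(cm, m)/var(cm) = 1, so the leak is a/(a+b). At ρ = .6:

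- Binary 50%, 0.3 SD between categories: a = 0.125/0.8 = 0.156, b = 0.0195, leak 0.889, estimate 0.267, SE 0.178, z = 1.50, rate 32%. Simulated: 32%.
- Anxiety, 0.3 SD per SD: a = 0.5/0.8 = 0.625, b = 0.25/3.2 = 0.078, estimate 0.267, SE 0.089, z = 3.0, rate 85%. Simulated: 79–82%, with scores truncated at zero and the residual variance estimated.

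Without centring, the simulated rates by this route are 24% and 42%. With time, condition and moderator all centred they are 4–5%, and with the two-way terms included they are 5–6%.

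**The case against.** The strongest reply is that naming the highest-order interaction is ordinary shorthand for a full factorial model, and that most interaction syntax adds the lower-order terms by default. The contrast with the outcome models is also weak evidence: with two predictors, time × condition is both the only interaction and the highest-order one. This stands as a possible reading, since the text does not say that two-way terms are left out. It does not say that they are included either, and the two readings give different tests, one of them invalid.

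A reader might infer that a real condition effect will be reported as moderation for every moderator. The documents do not support that. The inflation needs the literal reading and a particular coding. For the leak from the condition effect, a mean-centred moderator, or a balanced binary one coded −1/+1, keeps the rate near 5%. Where inflation occurs it is a probability that depends on prevalence and on which category is coded 1.

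Nor does the problem simply grow with the trial's success: the time × moderator route operates with no condition effect at all.

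It also stands that no stated hypothesis concerns moderation, and that the Aim 1 and Aim 2 models include their time × condition term.

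**Conclusion.** The point holds as a specification fault in the moderator models only. As written they list no two-way interactions, coding or centring, and a literal fit can turn an effect on change into apparent moderation. For a 0.3 SD condition effect the false-moderation rate is about 12–46% with 0/1 binary moderators and about 34–53% with an uncentred anxiety sum. For a 0.3 SD time × moderator effect with the moderator centred, it is roughly 30–80%. The full model gives about 5%.

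These sizes rest on the assumptions listed in the working, none of which the documents supply beyond N, the error rate and the two time points. Independence of moderator and condition is the least secure for self-disclosure. If it occurred for 30% of researcher-only and 80–90% of KOL caregivers (an assumption), simulated false moderation is 42–50% under the literal model and about 5% under the full one.

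The Hypothesis 1a test is unaffected. The change should be made, but it does not bear on the main conclusions.

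**What to change.** Replace the moderator sentence with one stating that each model contains time, condition, the moderator, all three two-way interactions and the three-way interaction, with the same random effects as the outcome models. State the coding of time, condition and each categorical moderator, and mean-centre continuous moderators. The two-way terms correct the test; coding and centring then serve to make the lower-order coefficients interpretable.

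The cost is one SAP sentence and, for a binary or continuous moderator, three extra parameters per model. The SAP reports pre/post data from 17 participants and no analysis as of 8/11/21, so at that date the clarification could be made without knowledge of results.
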